If interest is shown, the study recruiter will first inquire about their age and pregnancy status as the study only allows those who are 18 years of age and older and not currently pregnant. Upon finding individuals who are under 18 or are pregnant the recruiter will inform them they are not eligible, thank them for their time, and record the reason for non-participation in the study database. For individuals who are 18 or older and are not pregnant, the recruiter will invite them to a private space where they will be asked (non-identifying) demographic and socioeconomic questions. The demographic and socioeconomic questions asked to all potential participants will allow the study team to perform a comparison later to determine what differences there are between smartphone owners and non-owners, and how generalisable the results are. Following the demographic and socioeconomic questions will be a number of inclusion and exclusion criteria questions to confirm the remaining eligibility criteria (smartphone ownership, literacy, photo proof of identification, willingness to participate). If an individual is found to be ineligible the recruiter will inform them they are not eligible, thank them for their time, and record the reason for non-participation in the study database. If the reason for exclusion is that they do not own an Android phone with data, the type of phone will also be noted.

Patients who fit the study eligibility criteria will be invited to participate, provided a broad overview of the study, explained the randomisation, read the informed consent documentation, and asked to sign it after being told that participating requires them to allow the study team to monitor their laboratory results throughout the study and contact them with a follow-up questionnaire about their experiences of the study and HIV care they received. At any time, if an individual decides they do not want to participate, the recruiter will thank them for their time, and record the reason for non-participation in the study database.

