Upon signing informed consent, their personal details including name, surname, ID number, and a baseline survey which consists of a HIV/CD4 count knowledge questionnaire (all tools listed in appendix II) will be recorded into REDCap (Harris et al, 2009), an electronic data capture tool hosted at Wits University², using a tablet device by trained research staff. At the end of the recruitment process all patients will be provided their R50 participation allowance. Patients in both study arms will be encouraged to return to the clinic as per the clinic guidelines to receive their CD4 result and attend wellness or HIV care follow-up.

REDCap will randomise the participant to the standard of care or intervention arm through the device without informing the participant. Participants randomised to the standard of care arm will be provided with a copy of their signed informed consent document and thanked for their time.

Participants randomised to the intervention arm will be told about the smartphone app and told how it works. The study staff member will install the app on the participant's phone and assist the participant in setting up an account with a username, password and PIN number and provide an overview of how the app and notification system works. Participants will be

² REDCap (Research Electronic Data Capture) is a secure, web-based application designed to support data capture for research studies, providing: 1) an intuitive interface for validated data entry; 2) audit trails for tracking data manipulation and export procedures; 3) automated export procedures for seamless data downloads to common statistical packages; and 4) procedures for importing data from external sources.

informed that they are welcome to use the app at any time, and it will notify them when a laboratory result has arrived. As mentioned above, the cost per laboratory result received is approximately R0.02. Patients will be informed of this cost prior to participating.

[figure not shown]

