Appendix II: Participant survey tools

	Population survey (To be given to all newly diagnosed HIV-positive patients that have had CD4 count bloods drawn)
1	Recruitment Date:
2	Recruitment site:
3	Gender:
4	Date of birth:
5	Marital status:
6	Suburb currently living in:
7	Country of birth:
8	Highest education received:
9	What is your current employment status?
10	Usual monthly household income: (Note: still being reviewed based on discussions around Proxy Means Test method)
11	Preferred language for reading:
12	Do you share your phone with someone?: Y/N
13	Do you own a smartphone? Y/N
14	Do you use data on your smartphone (eg: WhatsApp, WeChat, Mxit, web page, email)?

	Recruitment survey (To be given to all eligible and willing participants)
1	First name:
2	Last name:
3	Phone number:
4	SA ID, Passport or refugee number:
5	Lab Specimen ID number:

6	WHO staging on patient chart: 1, 2, 3 or 4
---	--

	Reason for ineligibility survey (To be given to ineligible patients)
1	Age - Under 18
2	Phone - Not Android/Not working/Not active
2a	Type of phone:
3	No photo proof of identity
4	Cannot read English or Zulu
5	Not willing/unable to sign informed consent
6	Pregnant
7	Refused to participate

	HIV/CD4 Count/VL knowledge All answers are true/false (Correct answer in parentheses) (To be given at baseline and end of study for all participants)
1	A healthy-looking person can have HIV. (True)
2	Coughing and sneezing DO NOT spread HIV. (True)
3	A person can get HIV by sharing a glass of water with someone who has HIV. (False)
4	A woman can get HIV if she has anal sex with an HIV positive man. (True)
5	Showering, or washing one's genitals/private parts, after sex keeps a person from getting HIV. (False)
6	A pregnant woman infected with HIV and taking medicines will always have a baby born with HIV. (False)
7	People who have been infected with HIV quickly show serious signs of being infected. (False)
8	A woman cannot get HIV if she has sex during her period. (False)
9	There is a female condom that can help decrease a woman's chance of getting HIV. (True)

10	A person will NOT get HIV if she or he is taking antibiotics. (False)
11	A person can get HIV from oral sex. (True)
12	HIV can be transmitted through vaginal sex without condoms. (True)
13	HIV cannot be transmitted through use of public toilets. (True)
14	HIV cannot be transmitted through sweat. (True)
15	Use of birth control pills cannot prevent people from getting the HIV/AIDS virus. (True)

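### The survey taken before signed consent is described as non-identifying but records full date of birth with suburb; age in years would serve every stated use

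*Protocol*

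**What the plan says.** **Order of steps.** Under Methodology, Recruitment, the protocol has staff inform patients about the study and invite them to pre-screening. Then: "If interest is shown, the study recruiter will first inquire about their age and pregnancy status". Those who pass are taken to a private space, where "they will be asked (non-identifying) demographic and socioeconomic questions". The remaining eligibility questions follow, then the study overview and the consent form. Direct identifiers come only after that: "Upon signing informed consent, their personal details including name, surname, ID number".

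**The form.** Appendix II heads the first tool "Population survey (To be given to all newly diagnosed HIV-positive patients that have had CD4 count bloods drawn". Besides date of birth, it asks for recruitment date, site, gender, marital status, "Suburb currently living in", "Country of birth", education, employment, income, language and phone use. Name, phone number, ID number and laboratory specimen number are in a separate recruitment survey for eligible and willing participants, which has no date-of-birth item.

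**People who do not join.** For someone found ineligible, "the recruiter will inform them they are not eligible, thank them for their time, and record the reason for non-participation in the study database". A reason is also recorded for anyone who decides not to take part. The same section says the demographic answers of all potential participants will be used later to compare smartphone owners with non-owners and to judge how far the results generalise.

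**Date of birth elsewhere.** The Appendix III table lists date of birth (for people without a South African ID number) and gender among the enrolment details that link a patient to the NHLS database. SAP 6.4.1 derives age from date of birth.

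**The concern.** The Recruitment text holds names and ID numbers back until consent is signed and describes what is asked before then as not identifying anyone. The form does not match that description. A full date of birth combined with sex and suburb can point to one person, and every record in this survey carries an HIV diagnosis. Those affected include people who turn out to be ineligible or who decline.

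Accidental disclosure is the main subject of the protocol's Safety considerations, but the measures there concern the app. A participant who withdraws has their data removed from REDCap (Participant opt-out). No equivalent step is described for someone who never enrols. De-identification is promised for participant data at analysis (Data management), and it is unclear whether that reaches fields already labelled non-identifying on people who are not participants.

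**Working it through.** The plan gives no figure on this point, so there is none to reproduce. The first check is textual; the second is an illustration of size.

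**1. The passages side by side**

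- Recruitment describes the questions as non-identifying. The Appendix II form for that step includes full date of birth and suburb.
- Appendix III uses date of birth to match a person to laboratory records. A field that serves as a matching key is not non-identifying in the protocol's own usage.
- On who is surveyed, Recruitment limits the questions to people who show interest, are 18 or older and are not pregnant. The Appendix II header says "To be given to all newly diagnosed HIV-positive patients that have had CD4 count bloods drawn". Read literally, the header also takes in people under 18, pregnant women and people who showed no interest. The two cannot both be followed.

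**2. How many people would be unique**

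Inputs from the protocol (Population): catchments of about 220,000 (Hillbrow) and 250,000 (Helen Joseph), and an unofficial area population of over 900,000, taken as 900,000.

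Assumptions not in the documents: 70% of the population are adults; ages span 30 to 50 years; there are 5 to 20 suburbs; people are spread evenly over the cells.

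Mean adults per cell: m = 0.70 × N / (365.25 × years × 2 sexes × suburbs). Chance that a person shares the cell with nobody: exp(−m).

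| Case | m | Unique |
|---|---|---|
| N = 250,000; 30 years; 5 suburbs | 175,000 / 109,575 = 1.60 | 20% |
| N = 220,000; 50 years; 20 suburbs | 154,000 / 730,500 = 0.21 | 81% |
| N = 900,000; 30 years; 5 suburbs | 630,000 / 109,575 = 5.75 | 0.3% |
| N = 900,000; 50 years; 20 suburbs | 630,000 / 730,500 = 0.86 | 42% |
| N = 250,000; 30 years; suburb ignored | 175,000 / 21,915 = 7.99 | under 0.1% |
| N = 220,000; 50 years; suburb ignored | 154,000 / 36,525 = 4.22 | 1.5% |

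**3. The same calculation with age in years**

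Dropping the factor 365.25 gives 154,000 / (50 × 2 × 20) = 77 adults per cell at the low end and 175,000 / (30 × 2 × 5) = 583 at the high end for the stated catchments. At 900,000 the range is 315 to 2,100. With m = 77 or more, exp(−m) is effectively zero. Under these assumptions the exact birth date accounts for almost all of the uniqueness on these three items, and suburb can stay once it is gone.

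Country of birth is left out because the documents give no distribution. A rare country of birth would make a record more distinctive in either version.

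**4. What the planned analyses need**

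SAP 7.2 and 7.3 tabulate age, education, LSM and employment, with gender in 7.2. The protocol's subgroup (18 to 25 years), the SAP's priority group (18 to 30) and the 5-year age bands of the cost-effectiveness analysis can all be formed from age in completed years. No table uses an exact birth date for people who did not enrol.

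**The case against.** The strongest reply is that non-identifying can fairly mean free of direct identifiers. On that reading the plan is consistent: name, phone, ID and specimen numbers all wait for consent. Re-identification would need both access to the database and outside data. Data management and Regulatory compliance describe encrypted transmission, a password-protected encrypted database and de-identified analysis. The percentages rest on assumed values and fall to 0.3%, or to 1.5% or less if suburb is ignored. No endpoint, power calculation or estimate is touched.

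Much of this stands. The risk is indirect, applies to some people and cannot be sized from the documents. The reply does not explain why a field used in Appendix III as a matching key belongs in a survey described as non-identifying. Encryption limits who can see the data; it does not make the description correct.

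A reader might also infer several stronger points that the documents do not support:

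- *That nobody surveyed gave any permission.* Patients are informed and invited to pre-screening first, and the consent pages are not in the review copy. A verbal or screening consent cannot be ruled out; only the order relative to signed study consent is established.
- *That everyone newly diagnosed is surveyed.* The Appendix II header says so, but the Recruitment text is narrower.
- *That the ethics committee approved one text while recruiters use another.* The protocol describes ethics review as still to come, and both texts are in the same protocol.
- *That at least 350 to 525 non-participants are affected.* This comes from 350 / 0.50 = 700 and 350 / 0.40 = 875, less the roughly 350 whom SAP 5 expects to recruit. The 40-50% phone figure is a Hillbrow estimate, SAP 4.1 lists four sites, and those surveyed have already shown interest. It is not a minimum.
- *That suburb must be removed or coarsened.* The stated use includes generalisability, SAP 5 names residence among the eligibility criteria, and the calculation with age in years shows no need.

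**Conclusion.** The point holds as an inconsistency between the Recruitment text and the Appendix II form, with an avoidable disclosure risk attached. Before signed study consent the form takes full date of birth together with other indirect identifiers from people known to be newly HIV-positive, under a description that does not fit. Some who are ineligible or decline could be re-identified by someone holding the database and outside information. That their answers are kept is an inference from the planned owner versus non-owner comparison; the text states outright only that the reason for non-participation is recorded.

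The share unique on date of birth, sex and suburb is about 20% to 81% in the stated catchments and 0.3% to 42% at 900,000, given the assumed adult share, age span, number of suburbs and even spread. These figures show that the risk is realistic, not how large it is. The trial's results are unaffected. The change is worth making because it is nearly free and removes most of the risk.

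**What to change.** 1. In the Appendix II population survey, replace date of birth with age in completed years. The recruiter already asks age at the first screening question.
2. Add date of birth to the post-consent recruitment survey. SAP 6.4.1 can then derive age for randomised participants, and the Appendix III linkage has the field it needs.
3. SAP 4.3 and 5 show that randomisation and recruitment had begun. For any records already held on people who did not enrol, convert date of birth to age at the recruitment date and delete the original.
4. Leave suburb as it is.
5. Reconcile the Recruitment text with the Appendix II header so that one statement defines who is given the survey.

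The cost is one REDCap field replaced, one added, one recode of existing records and a wording correction. The comparison of owners with non-owners, the generalisability assessment and the SAP tables can all be run as planned.

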5. To specifically look at 2 subgroups – men and young adults (18 to 25 years of age), who would particularly benefit from improved linkage to care.
6. To assess the performance of the app in clients with different levels of education and standard of living, and see if there are differences in clinical and usage outcomes
7. To evaluate differences in linkage-to-care, HIV-knowledge, adherence to medication (treatment patients only) and reported quality of life between wellness and treatment patients.
8. To assess the financial and economic costs of providing the SmatLtC smartphone app.
9. To determine the incremental cost, and cost-effectiveness of ART initiation link to the smartphone app (receiving laboratory results and linkage-to-care) as compared to the standard ART initiation.

Study design

Population

The study was designed to take place in two high-volume HIV testing sites in Johannesburg, South Africa. To ensure a sufficient sample size for the study results to be statistically significant, the study sites required a minimum of 1000 new HIV-positive patients per month. According to the District Health Information System, there are three possible sites within the province of Gauteng, where Johannesburg is situated; Chris Hani Baragwanath Hospital, Hillbrow Community Health Centre (CHC), and Helen Joseph Hospital. The study team selected Hillbrow CHC and Helen Joseph Hospital due to their proximity to each other, ease of access and the fact that no similar research activities are ongoing in either site.

Hillbrow CHC is an inner-city clinical site which provides primary, HIV, antenatal care (ANC) and postnatal care (PNC) care to patients. Johannesburg's inner-city is characterised by high density living, a large immigrant population and high rates of poverty and unemployment. While official population estimates cite Johannesburg's population as 400,000 individuals, unofficial population estimates suggest that over 900,000 individuals currently live in the area (O'Connor et al, 2011). The official catchment population for Hillbrow CHC is approximately 220,000 from around Hillbrow and surrounding neighbourhoods. Despite the poverty, smartphone ownership for those attending care at Hillbrow CHC is approximately 40-50%. HIV prevalence levels are approximately 22%.

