Helen Joseph Hospital is approximately 4 km west of Johannesburg's inner-city in the suburb of Auckland Park. As a tertiary clinical site, the hospital provides a number of clinical services including HIV, ANC, PNC, and specialised care services to patients and has a connection with the University of Witwatersrand's Department of Medicine. The area surrounding Helen Joseph Hospital is comprised of mostly black South African middle-income families living in single unit residential dwellings. Helen Joseph Hospital has a catchment population of around 250,000 and an HIV prevalence of approximately 15-20%.

Linkage-to-care rates for all newly diagnosed HIV-positive individuals in both sites are 50-55%. Women have slightly higher linkage rates, at 60%, while men have slightly lower rates, close to 45%. Exact linkage-to-care figures for young adults, those aged between 18 and 25, in this area are unknown. However, previous research has suggested linkage rates for young adults to be 40-45% (Takuva et al 2015). Due to South African laws that protect exploitation of children and the resulting difficulty in including them in research studies, all participants will be 18 years of age or older.

Intervention

This is a multi-site randomised controlled trial in which newly diagnosed HIV-positive patients, fulfilling all inclusion criteria, will be randomised to either receive the intervention (installation of a password-protected laboratory result and HIV-information app on their smartphone) or the standard of care. All patients will be provided with their unique identifier, to present to the clinic, and asked for permission to access their results on the computer, as a means to assess follow up, to phone them and ask them about their experience of HIV care (at the end of the study) and to verify their clinic attendance throughout the study. Participants will be able to provide feedback about the study to the study team by phone or SMS at any time. In return for their time all study participants will receive a R50 study participation allowance, in the form of a mobile phone credit voucher, at the end of their recruitment visit. Participants will be informed that no additional funds will be provided for subsequent appointments.

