The aim of the study is to show that smartphone apps work for that proportion of the population that currently have Android smartphones, not that it works for the general population. Smartphone purchase is rapidly increasing in South Africa, with 75% of new cell phones sold in South Africa currently being smart phones. We expect that randomization and a large sample size will enable us to have a reasonable balance between the arms, unless participants randomized to the control group request study withdrawal due to not getting the app.

Sample Size

Based on a primary endpoint of a second HIV-linked laboratory test (CD4, viral load) being performed at a clinical facility, within 8 months after the HIV-positive result, suggesting successful attendance and entry into HIV care, we anticipate at least 1000 patients in each arm will be needed. The study team expects to see a 20% difference in linkage to care levels through the app (using a second HIV-linked laboratory test as an indicator for linkage to care). The sample size is calculated based on 80% power, 0.05 significance with a loss-to-follow-up rate of approximately 27% (Hillbrow CHC data). Both ART and pre-ART patients will be expected to return for a follow-up laboratory test around 6 months after diagnosis; ART patients for a viral load, and pre-ART for a follow-up CD4 count.

In South Africa, both younger and male clients have lower linkage to care rates than females and individuals over 25. In order to conduct subgroup analysis on these higher-risk populations (young people and men), there will be an over-sampling of male patients and those between the ages of 18 (the age of majority) and 25 for both the intervention and control arms given that it has been shown that these groups are less likely to access health services efficiently (Kranzer, 2010). These populations will be recruited until 250 of these individuals are included in both arms to ensure the study is powered to analyse the effect in these key subgroups. Based on a 20% difference in linkage to care for the intervention/app arm with an 80% power, a significance level of 0.05 and a loss-to-follow-up rate of 40% a sample size of 97 per arm is required. Again, the study team will over-sample based on the proof-of-concept nature of the study.

Figure 2: *Recruitment flow chart*

App specifications

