The primary outcome, linkage to care around 6 months after initial diagnosis, will be available after the final patient recruited has reached the 8 month mark, allowing immediate assessment of the feasibility and immediate impact of the app on initial linkage to care. Thereafter, retention in care, defined as continuation of HIV care (regular clinic visits with laboratory tests and/or medicine pickup) after the linkage to care visit will be assessed 12 months after linkage to care had been made.

Analysis will be done by the study team using STATA. Intention-to-treat will be the primary approach of the analysis and all missing data points will be considered to be loss-to-follow-up. Analysis of the primary outcome will be based on a chi-squared test comparing the proportion of individuals between the study arms and within study sites. A

logistic regression model, with linkage to care as the dependent variable, will be a secondary analysis of the primary outcome.

For secondary outcomes, chi-squared tests will be used for binary variables, Mann-Whitney-U tests for non-normally distributed variables, and t-tests for continuous variables. Relative risk calculations (at 95% confidence) will be used to compute binary variables. Survival analysis will be conducted to determine linkage outcomes at 6 months. A sensitivity analysis will be conducted using regression analysis to identify and adjust for potential confounders.

For the cost-effectiveness analysis, we will have data on direct costs and understand the resource requirements for the development of the app. We will corroborate our existing estimates of the smartphone data costs of the patient. The study team will collect data on clients' opportunity cost as part of the end of the study participant interview as linkage to care (as opposed to non-linkage to care) actually takes more time. We will use primary data collect through this study to calculate unit costs associated to providing HIV services.

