4.3 Randomisation and blinding

4.3.1. Patients were randomised through the REDCap system with no blinding

5. SAMPLE SIZE

Recruitment for this trial showed that achieving a sample size for any sub-group analysis is difficult to achieve with an app limited to a subset of smartphones in circulation and several other eligibility criteria on age, residence, literacy, and having a smartphone with data. Section 7.1. shows the flowchart of the HIV cases as they are screened and assessed for eligibility, then randomised and followed up. Priority groups of interest to this trial are males and young HIV clients aged 18-30 years, and it is exactly these two groups which are also more difficult to screen for eligibility as they use HCT services to a lesser extent.

The recruitment over approximately 8 months is expected to be able to recruit about 350 individuals. While it would be desirable to recruit a larger sample, as decision was made to stop at a time when sufficient sample is achieved to detect any effectiveness of the app (based on a 20% difference in linkage to care between the intervention and control arm, an 80% power with significance level of 0.05). At this sample size, it will be possible to see any trends in linkage to care in the priority sub-groups (males, youth) between the two trial arms, but the sub-groups will not be large enough to detect a 20% difference with statistical accuracy.

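### The Protocol's stated need for at least 1000 patients per arm does not follow from its own inputs, and it conflicts with SAP section 5, which accepts about 350 in total on the same difference, power and alpha

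*Protocol*

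**What the plan says.** The Protocol's Sample Size section states for the primary endpoint that "we anticipate at least 1000 patients in each arm will be needed". It gives the effect as follows: "The study team expects to see a 20% difference in linkage to care levels through the app". It gives the basis as "The sample size is calculated based on 80% power, 0.05 significance with a loss-to-follow-up rate of approximately 27" per cent. No control rate appears in that section, and it does not say whether 20% is absolute or relative. The only control rate for all patients is in the Population section: "Linkage-to-care rates for all newly diagnosed HIV-positive individuals in both sites are 50-55" per cent.

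The same Sample Size section gives 97 per arm as required for the male and young-adult subgroups, with the same 20% difference, power and alpha and a stated 40% loss. It ends by saying that the team will over-sample because the study is a proof of concept.

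SAP section 5 says: "The recruitment over approximately 8 months is expected to be able to recruit about 350 individuals". It justifies stopping there by a 20% difference, 80% power and 0.05 significance, and concedes that the subgroups will be too small. It mentions neither the 1000 per arm nor the 27% loss.

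**The concern.** A size presented as needed and as calculated should be recoverable from the inputs listed beside it. This one is several times larger than those inputs require. The two documents then reach incompatible conclusions from one set of criteria: 2000 patients are required in one, and about 350 (17.5% of 2000) suffice in the other.

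This matters for interpretation. A reader holding only the Protocol would take the trial to be far below its requirement. A reader holding only the SAP would take its adequacy as settled. Which is nearer the truth depends on the meaning of 20% and on how loss is treated, and neither document fixes these.

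**Working it through.** **Inputs.** Control linkage p1 = 50-55% (Protocol, Population). Difference 20%, power 80%, alpha 0.05, loss 27% (Protocol, Sample Size). Two-sided, because the alternative in SAP section 3.3 is inequality. Chi-squared comparison of two proportions (Protocol, Analysis plan). Equal allocation is an assumption; the Protocol gives the same number for each arm.

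**Formula.** With p̄ = (p1 + p2)/2,

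n per arm = [1.960·√(2p̄(1−p̄)) + 0.8416·√(p1(1−p1) + p2(1−p2))]² / (p2 − p1)²,

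then divide by 1 − 0.27 = 0.73 and round up.

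*Worked case, 50% v 70%.* p̄ = 0.60. The first term is 1.960·√0.48 = 1.358 and the second is 0.8416·√0.46 = 0.571. The sum squared is 3.720, and 3.720/0.04 = 93.0. Divided by 0.73, this is 127.4, so 128.

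| Reading of 20% | Rates | n before loss | n after 27% loss |
|---|---|---|---|
| Absolute | 50% v 70% | 93.0 → 93 | 127.4 → 128 |
| Absolute | 55% v 75% | 88.1 → 89 | 120.7 → 121 |
| Relative | 50% v 60% | 387.3 → 388 | 530.6 → 531 |
| Relative | 55% v 66% | 308.8 → 309 | 423.1 → 424 |

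A continuity correction raises the after-loss figures only to 135-142 (absolute) and at most 559 (relative). The stated 1000 is not reproduced.

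**What 1000 per arm would detect.** At 80% power from 50-55% control linkage, 1000 per arm detects about 6 points. With 1000 × 0.73 = 730 evaluable, it detects about 7 points.

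**Which reading the Protocol favours.** The subgroup figure of 97 is reproduced exactly by 40% v 60% (96.9 → 97) with no inflation for loss. The Population section puts young-adult linkage at 40-45%. A relative 20% from 40% (40% v 48%) would need 604. The 97 therefore points to absolute points. Dividing 96.9 by 0.60 for the stated 40% loss would give 162, so the loss was apparently not applied there.

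**If lost patients count as failures on top of the Population rates.** Multiply each rate by 0.73. Absolute: 36.5% v 51.1% needs 181, and 40.2% v 54.8% needs 183. Relative: 707 and 600. These also fall short of 1000.

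**Power of the SAP's sample.** Take 350/2 = 175 per arm, and 175 × 0.73 ≈ 128 after loss.

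Power = Φ{[|p2 − p1|·√n − 1.960·√(2p̄(1−p̄))] / √(p1(1−p1) + p2(1−p2))}.

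For 50% v 70%, n = 175: (0.20 × 13.229 − 1.358)/0.678 = 1.90, so power is 97%.

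| Reading | 175 per arm | 128 per arm (27% lost) |
|---|---|---|
| Absolute, control 50-55% | 97-98% | 91-92% |
| Relative, control 50-55% | 47-56% | 36-44% |
| Absolute, 27% lost counted as failures | 78-79% | not applicable |

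**The case against.** The strongest reply is that nothing is harmed: 1000 is a floor above any requirement computed here, and the SAP later lowered the target with reasons (slow recruitment, narrow eligibility) while admitting the subgroup shortfall. Much of this stands. An over-large target does not damage power, type I error or the estimate, and a later plan may revise an earlier one. It does not explain how the same difference, power and alpha support both numbers, or where the 27% loss went.

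The 1000 can be approached, but only by giving an input a role that the main calculation does not give it. Using 27% as a failure rate cut by a fifth (27% v 21.6%) gives 990. Using 40% v 48% with the subgroup's 40% loss gives 604/0.60 ≈ 1007. These are conjecture.

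A reader might infer four stronger things that the documents do not support:

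- **That 350 is far too few.** On the absolute reading it exceeds the total of 242-256 (2 × 121 to 2 × 128). It is short for the main comparison if 20% is relative, and marginal if losses count as failures on top of the stated rates.
- **That 1000 was a voluntary over-sample.** The over-sampling sentence closes the subgroup paragraph. Its link back to the main figure is unclear, and the main paragraph presents 1000 as a calculated need. Only the sponsor can confirm this.
- **That inflating for 27% loss is an error.** The outcome is read from the laboratory database, so a non-returner could simply count as not linked. But the Analysis plan says only that "all missing data points will be considered to be loss-to-follow-up", SAP 6.7.1 says much the same of withdrawals, and the Participant opt-out section removes a withdrawn person's data from REDCap. Truly missing outcomes are possible.
- **That the per-arm figure drove site choice.** The Population section says "the study sites required a minimum of 1000 new HIV-positive patients per month". That is a monthly site volume and is not tied to 1000 per arm.

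**Conclusion.** The concern holds in this form: the stated requirement of at least 1000 per arm is wrong as a calculated need, and it conflicts with SAP section 5. On the Protocol's inputs the requirement is about 121-128 per arm for 20 absolute points, so the stated figure is roughly eight times too large (1000/128 = 7.8; 1000/121 = 8.3). For a relative 20% it is about 424-531, so the stated figure is roughly twice too large (1000/531 = 1.9; 1000/424 = 2.4). These results assume 50-55% control linkage, a two-sided test, equal arms and inflation by 1/(1 − 0.27).

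The absolute reading is favoured by the subgroup figure but is not stated. The consequence lies in interpretation: the reduced trial is well powered on the absolute reading unless losses count as failures on top of the stated rates, when it is marginal at 78-79%. On the relative reading it is clearly underpowered.

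**What to change.** This costs wording in two sections and no extra patients.

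1. **Protocol, Sample Size.** Replace the 1000 with the recomputed requirement. State the 50-55% control rate, the two-sided test and, if the sponsor confirms that this was the design intention, that 20% means absolute points. The requirement is then about 121-128 per arm with 27% loss. It is 89-93 if non-return counts as not linked and the Population rates already include non-returners.
2. **Over-sampling.** Give any recruitment above the requirement as a separate number with its reason.
3. **Loss rule.** Say whether a patient with no second test counts as not linked or as missing, how withdrawn patients are treated, and whether the 50-55% already includes non-returners. Use the same rule in the Protocol and SAP.
4. **SAP section 5.** Carry the same required number, acknowledge the dropped 1000 per arm, and give the power of about 175 per arm: 97-98% for 20 absolute points, 91-92% after 27% loss, and about 78-79% if the lost 27% count as failures on top of the stated rates.
5. **If 20% was meant as relative.** Report 47-56% power (36-44% after loss) and withdraw the statement that the sample is sufficient.
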